# 21. STATISTICAL ANALYSIS

## 21.1. General considerations

An analysis of Part A will be conducted when all subjects in Part A have completed Part A.

A final analysis of Part B will be conducted when all subjects have completed Part B.

The statistical analysis principles described below will be supplemented by a comprehensive statistical analysis plan (SAP) which will be finalised before the database is locked. This will contain details of methods for handling missing data and early withdrawals. Any changes to the statistical analysis plan will be described and justified in the final report.

Descriptive statistics will be used to analyse the data in both Part A and Part B of the study. The descriptive summary for the categorical variables will include counts and percentages. The descriptive summary for the continuous variables will include number of participants (n), means, medians, standard deviations, and minimum and maximum values. Pharmacokinetic measures will be analysed as for continuous variables.

In Part A and Part B, data will be tabulated and analysed with respect to subject enrolment and disposition.

In Part A, demographic, baseline characteristics and prior medications summaries will be presented overall. Concomitant medications, PD, PK and safety measure summaries will be presented by active treatment dose, placebo and overall. Note that results for the subjects on placebo across all doses will be combined for summary purposes.

---

In Part B, demographic, baseline characteristics (including history of lumbar radicular pain) and prior medications will be presented by treatment sequence and overall. Efficacy, PD, PK, concomitant medications and safety measure summaries will be presented by treatment within each treatment period and overall.

As this is a Proof-of-Concept study, no formal statistical hypotheses are being specified although some may be investigated as part of the data presentation, in which case corresponding 95% confidence intervals will be presented for treatment differences and p-values of  $<0.05$  will be declared statistically significant. Treatment comparisons will take into account the paired nature of the treatment responses where feasible and treatment period order will be ignored in any treatment comparisons.

All data will be listed for all subjects to support each table and to present all data. All statistical analyses will be performed using SAS unless otherwise stated in the SAP.

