## 21.5. Analysis of efficacy data (Part B only)

The primary population for analysis of efficacy data is the PP population. All summary tables and results of statistical analyses will be presented for the PP population for all efficacy endpoints. In addition, all summary tables and results will be presented for the FAS population.

Individual pain score-time profiles for each treatment within each subject will be presented graphically. The difference between the VAS pain scores for “Pain Now” at each timepoint for LAT8881 compared with placebo within each subject will be estimated and presented graphically. The number of subjects, mean, standard deviation, minimum and maximum VAS pain score at each timepoint, change from baseline, difference between treatments at each timepoint and change from baseline difference between treatments will be presented for each treatment overall and within each treatment period.

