2.5 Changes to analyses from protocol

These changes relate to Part B of the study only.

Interim analysis:

The planned interim analysis after at least 10 subjects had completed the study was undertaken after 14 subjects completed the study. The rationale for including 14 subjects within the interim analysis was based on a number of factors, including:

- The observation that 2 of the subjects received less than the full dose (estimated to be 60-65%) due to technical issues with the infusion equipment. Both the sponsor and the PI agreed that it was wise to include at least an additional 2 subjects within the interim analysis
- At the time recruitment approached 12 completed subjects, the recruitment rate was relatively strong, which resulted in 14 subjects completing the study before the interim analysis was initiated.

The planned initial graphical outputs were produced.

No re-estimation of the sample size was undertaken. Based on: (i) the planned graphical outputs, (ii) some additional blinded post-hoc graphical presentations (not discussed in this SAP), (iii) the expectation that 17 subjects were expected to complete the study by 12 May 2023, (iv) dosing an additional 3 subjects to reach the target of 20 could take another 3-6 months, and (v) the inclusion of additional subjects would be unlikely to change any treatment signal in the data to such an extent that continuing recruitment is justified, the recommendation was made to close the study on 12 May 2023, with the last patient last visit then expected on 19 May 2023.

Final analyses:

The data presentation and analysis for the Bang Binding Index assessment has been included in this SAP as it was inadvertently missed in the previous version of the SAP.

After review of the interim analysis outputs where extensive variation in pain scores over time and an unexpected effect of being in the clinic for 24 hours possibly reducing pre-dose pain score on Day 2, particularly for pain at rest, the following decisions were made as to changes to the final analysis outputs.

- Pain at rest:
 - The mean change from baseline from 1 to 2 hours and from 4 to 6 hours are included to provide an easily interpretable summary measure of the pain response profile.
 - The area under the subject profile curve has been removed because it is less meaningful in a clinically useful interpretation of the pain response profile

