11.1.1 Biostatistical methods

Efficacy will be assessed based on the difference between treatments in the following measures:

Pain Now Scores (VAS)

“Pain now” scores, change from baseline, percentage change from baseline and summary scores (i.e. maximum change from baseline, mean change from baseline over 1 to 2 hours and mean change from baseline over 4 to 6 hours) will be listed for all study participants at each timepoint by treatment sequence.

Descriptive statistics including the number of participants, mean, standard deviation, median, minimum and maximum for the VAS “pain now” score at each timepoint along with the change from baseline and percentage change from baseline will be presented by treatment group within treatment period and overall. The mean, standard deviation, median, minimum and maximum for the change from baseline over 6 hours, the mean change from baseline over 1 to 2 hours and the mean change from baseline from 4 to 6 hours will be presented by treatment group within treatment period and overall.

Graphical presentations will include those presented for the interim analysis:

1. Individual subject VAS scores-time profiles by timepoint and by sequence (left panel LAT8881-Placebo, right panel Placebo-LAT8881)
2. Group mean VAS scores by timepoint and day, two sequences combined (one panel only)
3. Group mean VAS scores by timepoint and day in each panel, and by sequence (left panel LAT8881-Placebo, right panel Placebo-LAT8881)

Additional graphical presentations will include:

4. Individual subject change from baseline -time profiles by post-dose timepoint and by sequence (left panel LAT8881-Placebo, right panel Placebo-LAT8881)
5. Group mean change from baseline by post-dose timepoint by treatment, two sequences combined (one panel only)
6. Group mean change from baseline by post-dose timepoint and by sequence (left panel LAT8881-Placebo, right panel Placebo-LAT8881)
7. Difference between treatments in the change from baseline at each post-dose timepoint by sequence (left panel LAT8881-Placebo, right panel Placebo-LAT8881)
8. Difference between treatments in the change from baseline at each post-dose timepoint by treatment (one panel only)
9. A scatter plot for baseline scores with Placebo score on the x-axis, LAT8881 score on the y-axis, a diagonal line with slope=1 representing no difference between treatments will be overlaid on the plot, symbols and symbol colour will be used to identify treatment sequence.

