10. Maximum change from baseline will be presented using the same scatter plot format as for baseline scores
11. Mean change from baseline over 1 to 2 hours will be presented using the same scatter plot format as for baseline scores
12. Mean change from baseline over 5 to 6 hours will be presented using the same scatter plot format as for baseline scores

To estimate the difference between LAT8881 and Placebo in the change from baseline "pain now" VAS over all session time points, a generalised linear mixed effects model will be fitted. Fixed-effects will include treatment, session time point and period (i.e. Day) factors; baseline will be included as a covariate. Random effects for participants and participant by period will be included to take into account the repeated measures on each participant and the cross-over nature of the study. The covariance structure for the random effects is assumed to follow a compound symmetry structure. The estimated adjusted (least squares) mean change from baseline for each treatment at each session time, the difference between the treatments, the 95% confidence interval for the difference and the p value for the difference will be presented. A p value of <0.05 will be declared statistically significant. The model assumes no carry-over treatment effect and assumes that any period (i.e Day) effect will affect subjects in both treatment sequences in a similar manner.

The same model will be fitted to the change from baseline "pain on leg raise" VAS scores. As reflected in the scientific literature and regulatory authority guidelines, what constitutes a minimally significant change in baseline pain score can vary from subject-to-subject, whether the pain is acute or chronic, and on the mechanism of the pain. For the purposes of this study, the sponsor considers a 0.9 cm reduction to represent a minimally clinically significant change in pain as reported on the VAS, with the desired target reduction from baseline in the range of 0.9 to 3 cm.

Provocation Assessment with VAS

The pain on leg raise VAS score, change from baseline, percentage change from baseline, maximum change from baseline, mean change from baseline from 1 to 2 hours and mean change from baseline from 4 to 6 hours will be listed for all study participants at each timepoint by treatment sequence as for the "pain now" endpoints. Descriptive summary tables and analyses will be as per the "pain now" endpoints.

Patients general impression of change

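### Peak change and the two window means get per-treatment tables and paired plots, but no estimated within-participant difference or 95% confidence interval

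*SAP*

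**What the plan says.** The efficacy methods in SAP 11.1.1 open with: "Efficacy will be assessed based on the difference between treatments in the following measures". For the summary measures of pain at rest, the table text gives mean, SD, median, minimum and maximum for each treatment; for the late window, "the mean change from baseline from 4 to 6 hours will be presented by treatment group within treatment period and overall". Each measure also gets a scatter plot with placebo on one axis, LAT8881 on the other, a no-difference line and sequence-coded symbols: "Maximum change from baseline will be presented using the same scatter plot format as for baseline scores", "Mean change from baseline over 1 to 2 hours will be presented using the same scatter plot format as for baseline scores" and "Mean change from baseline over 5 to 6 hours will be presented using the same scatter plot format as for baseline scores". Leg-raise pain is handled the same way.

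SAP 2.4.2 makes peak change a secondary endpoint that compares the two arms. SAP 2.5 drops the area under the curve, which was paired with it, and adds the two window means "to provide an easily interpretable summary measure of the pain response profile".

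The only inferential analysis is a mixed model for change from baseline at the session time points, with treatment, time point, period and baseline as fixed effects. It reports a treatment difference, 95% interval and p value.

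For the by-time tables, protocol 21.5 says that "difference between treatments at each timepoint and change from baseline difference between treatments will be presented". Protocol 21.1 asks that comparisons use the pairing where feasible, and adds that "treatment period order will be ignored in any treatment comparisons".

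**The concern.** The stated basis for efficacy is a treatment difference, and peak change is defined as a comparison of arms. Yet the plan produces no numerical comparison for peak change or for the two window means. A reader gets each treatment's mean and SD and a plot of the pairs. The quantity a crossover is built to deliver, the within-participant difference with its precision, is left to be worked out by hand from the listings.

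Two declarations are also missing. The SAP's by-time table text gives score, change and percentage change per treatment, without the difference statistics of protocol 21.5. The SAP model adjusts for period, whereas protocol 21.1 says period order is ignored. SAP 2.5 lists changes from the protocol but mentions neither. At stake is whether these measures can be read as evidence for or against an effect, or only as description.

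**Working it through.** The plan states no precision or power figure, so there is none to reproduce. The check has three parts.

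**1. Can the planned outputs yield a paired interval?**
- *Point estimate: yes.* The tables are split by treatment within period, which gives four sequence-by-period means. With complete pairs, a difference follows by subtraction.
- *Precision: no.* With equal SDs, the SD of the paired difference is SD × √(2(1−r)). The tables give the SD but not r.
- *From the model: not as written.* Its response is the time-point change. No treatment-by-time term is listed, so the treatment difference is the same at every time. If such a term is intended, window-mean differences could be formed as contrasts. Peak change could not, because it is an extreme taken within each participant.

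**2. What is the interval worth?** Inputs: n = 17 expected completers (SAP 2.5). SD and r are assumptions, since the documents give neither.
- Columns read as independent groups: t(32) × SD × √(2/n) = 2.037 × 2 × √(2/17) = 1.40 cm.
- Paired: t(16) × SD × √(2(1−r)) / √n, with t(16) = 2.120 and SD 2 cm:
  - r = 0.3: 2.120 × 2.366 / 4.123 = 1.22 cm
  - r = 0.5: 2.120 × 2.000 / 4.123 = 1.03 cm
  - r = 0.7: 2.120 × 1.549 / 4.123 = 0.80 cm

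| Assumed SD (cm) | Independent groups | r = 0.3 | r = 0.5 | r = 0.7 |
|---|---|---|---|---|
| 1.5 | 1.05 | 0.91 | 0.77 | 0.60 |
| 2.0 | 1.40 | 1.22 | 1.03 | 0.80 |
| 2.5 | 1.75 | 1.52 | 1.29 | 1.00 |

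Adjusting for period with a 9/8 split uses t(15) = 2.131 and replaces 1/√17 = 0.2425 by ½√(1/9 + 1/8) = 0.2430. At SD 2 cm this adds at most 0.01 cm. For scale, SAP 11.1.1 takes a 0.9 cm reduction from baseline as minimally clinically significant.

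**3. What would ignoring period do?** Let D be the Day 1 minus Day 2 effect and n1 the number given LAT8881 first. The pooled LAT8881-minus-placebo mean is shifted by D × (n1 − n2)/n. Per 1 cm of D, that is 1/17 = 0.06 cm for a 9/8 split and 3/17 = 0.18 cm for a hypothetical 10/7 split. Half the between-sequence difference in mean Day 1 minus Day 2 change removes D.

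**A related inconsistency.** The late window is 4-6 h in SAP 2.5, SAP 3.2.2 and the listing and table text of SAP 11.1.1. It is 5-6 h in the SAP 11 parameter list and in figure item 12 of SAP 11.1.1. The SAP 3.2.2 formula averages only the 4 h and 6 h values, although 5 h is an analysis time point. The table text also refers to change over 6 hours without saying peak or maximum.

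**The case against.** The other side has a good deal of weight. A reader might infer that the arms are shown only in separate tables and that the crossover's pairing is thrown away. The documents do not support that. All three measures have subject-level paired scatter plots, and SAP 2.5 says the window-mean plots are there to show the pattern of treatment differences given a possible Day effect. Figure items 7 and 8 plot treatment differences in change at each time point. The mixed model, with participant and participant-by-period random effects, gives a treatment difference and 95% interval for both pain outcomes. The gap is confined to the derived summary measures.

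A reader might also infer that the SAP's own comparisons ignore period. They do not: the model includes it and the tables are split by it. The sentence about ignoring order is in the protocol. Nor does the SAP plan an independent-groups interval; the 1.40 cm figure is only a reference point. Unequal sequences are not certain either. Seventeen is an expected number, and the per-protocol set, primary for efficacy, may exclude participants with inadequate exposure.

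Protocol 21.5 speaks of time points, not summary measures, and SAP 3.2.4 refers to mock tables that are not among the documents, so the difference columns may exist there. Finally, SAP 3 calls the approach descriptive, with intervals if required, and protocol 21.1 sets no formal hypotheses.

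All of this limits the point without removing it. A descriptive study can still report an estimated difference and its precision. Protocol 21.1 itself calls for pairing where feasible, and for 95% intervals on treatment differences where hypotheses are investigated.

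**Conclusion.** The point holds for peak change, the 1-2 h mean and the late-window mean. The plan as written yields no paired estimate with its SD or 95% interval, and none of its planned tables or its model supplies one. The SAP's description of these measures as easy to interpret applies to the two window means only, not to peak change, and it does not rank them above other measures.

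The size depends on an SD and correlation that the documents do not give. Over the assumed ranges at n = 17, the paired half-width runs from 0.60 to 1.52 cm, against 1.05 to 1.75 cm for columns read as independent. The bias from ignoring period is small, about 0.06 cm per 1 cm of Day effect with a 9/8 split; the actual split and per-protocol number are unknown. Here the issue is mainly an undeclared conflict between protocol and SAP.

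This is worth correcting before the final analysis. It does not undermine the planned model for the primary time-point data.

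**What to change.** 1. Reconcile the late window first. Choose 4-6 h or 5-6 h throughout SAP 2.5, 3.2.2, 11 and 11.1.1, and say whether the 5 h value enters the mean. Name peak (maximum) change explicitly in the table text.
2. In SAP 11.1.1, for both pain at rest and leg-raise pain, report for each of the three summary measures the period-adjusted within-participant LAT8881-minus-placebo difference with its SD and 95% interval. The estimate is half the difference between sequences (LAT8881 first minus placebo first) in mean Day 1 minus Day 2 change. It rests on the no-carry-over assumption the SAP already makes.
3. Add the treatment-difference columns of protocol 21.5 to the by-time tables, or state in SAP 2.5 that the plots and model difference replace them, and why.
4. State in SAP 2.5 that treatment comparisons are adjusted for period, in place of the protocol 21.1 rule.

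The cost is a few table columns and short SAP edits. No new data are needed.

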11. EFFICACY (PART B ONLY)

Analysis Set: Full Analysis Set and Per Protocol population

Parameters:

- Pain now VAS score:
 - Change from Baseline to hours 0.25, 0.5, 0.75, 1, 1.5, 2, 2.5, 3, 3.5, 4, 5 and 6,
 - Percentage change from baseline to hours 0.25, 0.5, 0.75, 1, 1.5, 2, 2.5, 3, 3.5, 4, 5 and 6
 - Peak change from baseline over 6 hours
 - Mean change from baseline over 1 to 2 hours
 - Mean change from baseline over 5 to 6 hours
- Pain on leg raise VAS score:
 - Change from Baseline to hours 0.25, 0.5, 0.75, 1, 1.5, 2, 2.5, 3, 3.5, 4, 5 and 6,
 - Percentage change from baseline to hours 0.25, 0.5, 0.75, 1, 1.5, 2, 2.5, 3, 3.5, 4, 5 and 6

- Peak change from baseline over 6 hours
 - Mean change from baseline over 1 to 2 hours
 - Mean change from baseline over 5 to 6 hours
- Patients general impression of change at hour 6 on Day 1 and on Day 2
- Mechanical QST assessment using Von Frey Aesthesiometer
- Bang Binding Index assessment at 6 hours on Day 2

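### The efficacy model has no treatment-by-time term, so the adjusted means promised at each session time differ by one constant and cannot show how the treatment effect varies over time

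*SAP*

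**What the plan says.** SAP 11.1.1 (Pain Now Scores) sets out one inferential model. Its purpose is the LAT8881-placebo difference in change in "VAS over all session time points, a generalised linear mixed effects model will be fitted". The fixed part is: "Fixed-effects will include treatment, session time point and period (i.e. Day) factors; baseline will be included as a covariate". Random effects are participant and participant by period, and "The covariance structure for the random effects is assumed to follow a compound symmetry structure".

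The stated output is the adjusted "mean change from baseline for each treatment at each session time, the difference between the treatments, the 95% confidence interval for the difference"; a p value is also listed, followed by the rule "A p value of <0.05 will be declared statistically significant".

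The model is reused for pain on leg raise: "The same model will be fitted to the change from baseline". SAP section 11 lists the post-dose times for both outcomes: "Change from Baseline to hours 0.25, 0.5, 0.75, 1, 1.5, 2, 2.5, 3, 3.5, 4, 5 and 6", which is 12 times.

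Outside the model, SAP 11.1.1 gives descriptive statistics by timepoint and plots of the per-timepoint treatment difference (figures 7 and 8). Protocol 21.5 also asks for per-timepoint differences, descriptively.

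**The concern.** An additive model forces the two treatments' adjusted profiles to be parallel. The by-time means can show a time course common to both treatments, but not a treatment effect that rises and fades. Yet a changing effect is what the plan anticipates: the hypothesis in Protocol 6.1 refers to a peak of relief within six hours, and SAP 2.5 adds early and late window means to describe the response profile.

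This model supplies the only confidence interval for a treatment difference specified in SAP section 11; the descriptive statistics list none. If the SAP is followed to the letter, a by-time table repeats the overall result 12 times. If a programmer adds an interaction to make the table informative, the reported model is not the specified one, and 12 p values per outcome fall under the 0.05 rule. The wording does not settle which is intended.

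**Working it through.** The plan gives no figure to reproduce: SAP 2.2 and Protocol 7.3 state that no formal sample size calculation was done, and no SD is given.

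**1. Algebra.** With an identity link (assumed, since the SAP names none), the model is

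E[Y] = mu + tau(treatment) + theta(time) + pi(period) + beta x baseline.

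Adjusted mean on LAT8881 at time t minus that on placebo at time t = tau(LAT8881) - tau(placebo). Time, period and baseline cancel, so the difference does not depend on t. Neither random effect changes this.

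**2. Numerical check.** One simulated trial: 17 participants, 2 periods, 12 times, true effect -1.8 cm at 1, 1.5 and 2 h and zero elsewhere. Assumed SDs: participant 1.0, participant-by-period 0.7, residual 0.8.

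- Model as written: -0.255 at all 12 times.
- With treatment by time: -1.90, -1.49 and -1.38 at 1, 1.5 and 2 h, and between -0.14 and +0.52 elsewhere.

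The fixed-effect parameters rise from 15 to 26.

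**3. What the constant equals.** In complete data it is the simple average of the 12 time-specific effects. Take a treatment difference of 0.9 cm. The SAP gives this value as a reduction from baseline ("the sponsor considers a 0.9 cm reduction to represent a minimally clinically significant change in pain as reported on the VAS"), so using it as a treatment difference is an assumption.

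| Effect present at | Calculation | Shown at every time |
|---|---|---|
| 1, 1.5, 2 h | 3/12 x -0.9 | -0.225 cm |
| 0.5 to 4 h (9 times) | 9/12 x -0.9 | -0.675 cm |
| all 12 times | 12/12 x -0.9 | -0.9 cm |

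**4. Precision.** Assumptions: n = 17 (the completers expected in SAP 2.5), participant-by-period SD 1.2, residual SD 1.0, 15 degrees of freedom (t = 2.131).

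- Overall: SE = sqrt(2(1.2² + 1.0²/12)/17) = 0.423; half-width 2.131 x 0.423 = 0.90 cm.
- Single time: SE = sqrt(2(1.2² + 1.0²)/17) = 0.536; half-width 2.131 x 0.536 = 1.14 cm.
- Ratio 1.14/0.90 = 1.27; range 1.12 to 1.36 over participant-by-period SDs 1.0-1.5 and residual SDs 0.8-1.0.

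**5. If the overall interval is read as time-specific.** The figures below apply only on that reading (noncentral t, SE 0.423, 15 df).

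- Three-time shape, active times: the constant is off by 0.9 - 0.225 = 0.675 cm; coverage of the nominal 95% interval is 68% (57-77% over the SD range).
- Nine-time shape, active times: off by 0.9 - 0.675 = 0.225 cm; coverage is 92% (91-93%).
- At the times with no effect, the two coverage figures swap.

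**6. What adding the term brings.** Simulated by-time coverage (6,000 trials per scenario, 17 participants split 9:8, pooled compound-symmetry variance, no baseline covariate):

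- 95-97% when variance was constant over time, including under serial correlation.
- From about 100% at 0.25 h down to 88% at 6 h when the SD was assumed to grow from 1.07 to 2.07 cm; the overall contrast stayed at 95%.

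With no true effect, the chance that at least one of 12 by-time p values falls below 0.05 is about 22% (17-25% over the SD range).

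**The case against.** The strongest reply is that the model does what it is for. The aim is one difference over the session, an additive model estimates it, and the words for the difference, its interval and its p value are singular. On that reading the inference is sound and the by-time means are merely redundant. Timing is shown by the descriptive tables, the figures and the window means. The SAP calls its general approach descriptive, and the protocol specifies no formal hypotheses, so by-time intervals are not owed. Raw and adjusted differences would differ somewhat even under a constant effect, because of noise and the baseline and period adjustments.

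Much of this stands. The overall contrast is not in question, the study is exploratory, and the coverage figures apply only to a by-time reading. The mock tables mentioned in SAP 3.2.4 are not among the documents and might show what is intended. None of this removes the mismatch: adjusted means by treatment and time are promised from a model that fixes the gap between them in advance, and the text does not say that the difference is overall only.

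Two narrower objections do not hold. The primary endpoint's schedule implies 11 post-start times, with no 3.5 h measure, but SAP section 11 lists 12 for analysis; with 11 the illustrations become -0.9 x 3/11 = -0.245 and -0.9 x 8/11 = -0.655 cm, which changes nothing of substance. Nor does equal weighting bring in a new preference: it is what the additive model already estimates in complete data.

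**Conclusion.** The concern holds. Under the specified model and an identity link, the adjusted LAT8881-placebo difference is identical at all 12 session times for both pain outcomes. This follows from the model's form and needs no assumption about SDs or effect shape. The size of the distortion does: none if the effect is constant, and a 0.9 cm effect shown as 0.225 cm if it is confined to three of the 12 times. Those shapes, and every SD used, are assumptions.

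The consequence is limited. The overall contrast is unaffected, and unadjusted displays still show timing. What should be corrected is a by-time model output that cannot carry by-time information, together with the missing statement of what the interval and p value refer to.

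**What to change.** **Preferred.** Add treatment by session time to the fixed effects for pain now and for leg raise. For each, define the main contrast as the LAT8881-placebo difference averaged with equal weight over the 12 session times. Report the per-timepoint differences with 95% intervals as nominal, outside the rule for declaring significance.

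**Minimum alternative, if only the overall difference is wanted.** Keep the additive model, drop the by-time adjusted means, and state that the difference, interval and p value are the single overall ones.

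**Cost.** SAP wording plus one model term (11 further parameters), or wording alone for the alternative; no new data. In complete data the overall contrast and its power do not change. With the added term, by-time intervals are wider than the overall one and rely on compound symmetry, which would fail at late times if variability grows over the session. The 12 by-time p values per outcome are the reason for keeping those results nominal.
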